8.6 Off study criteria

Per Subject choice: Subjects may be removed from study at their request. The risks of withdrawing will be discussed, as will alternative treatment options.

Per principal investigator decision: Alemtuzumab (Campath®) administration will be discontinued; the subject will be followed until the event has resolved if the subject develops:

- Intolerance of alemtuzumab (Campath®) infusion as manifested by hypotension, fever, chills and/or rash that is refractory to supportive measures; OR any subject who develops CTCAE grade 4 hepatic injury or DIC subsequent to infusions of alemtuzumab.
- Life threatening acute hypersensitivity reactions
- Pregnancy or unwillingness to refrain from pregnancy
- Initiation of additional immunosuppressive therapy (except steroids or CsA)
- Failure to respond to Campath therapy
- Subject non-compliance
- Lost to follow-up

- Study completion

Those subjects who choose to withdraw or are removed from the study per PI decision will be asked to continue to have labs monitored through the 6 month off drug time point so that we can continue to monitor for post Campath related safety issues. Once off study subjects will be referred back to his or her referring physician or consented to the Hematology Branch evaluation and treatment protocol (94-H-0010) for consideration for standard therapy or evaluation for eligibility for another branch protocol, depending on what is considered to be in the best interest of the subject.

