2.2 Treatment options for T-cell large granular lymphocyte leukemia (T-LGL)

Most patients with T-LGL (>70%) require therapy because of recurrent infections, symptomatic anemia or severe thrombocytopenia. There is no standard approach to the treatment of these patients and optimum treatment remains undefined. The main goal of therapy is to ameliorate the cytopenia(s) to prevent life threatening infections, bleeding or complications from anemia. Case reports and case series in the literature have shown limited responses to steroids, low-dose daily cyclophosphamide, low-dose methotrexate or to granulocyte-colony stimulating factor (G-CSF)^{2,13,14,15}. Long-term intermittent treatment with these agents is often required, leading to toxicity and the potential for secondary leukemias or myelodysplasia (e.g., long-term alkylators use). Combination chemotherapy for patients with an aggressive clinical course has not been successful. Three case reports of patients with T-LGL leukemia have documented responses to daily cyclosporine A treatment, which appears to be better tolerated than the aforementioned drugs during potentially long-term therapy.^{16,17,18} At NHLBI we treated 25 T-LGL patients with oral cyclosporine and response was observed in about half of the patients. Sustained response required continued low-dose cyclosporine¹⁹. Despite improvement in the blood counts, increased populations of the CD3+ T-LGLs persisted in patients during cyclosporine therapy, suggesting an amelioration of the cytopenias by the drug as opposed to the eradication of the malignant clone.

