3. STUDY DESIGN AND METHODS

This is a pilot study of Phase II clinical trial design to evaluate the safety and efficacy of Campath in subjects with T-LGL leukemia. Alemtuzumab (Campath®) will be administered off label at 10 mg per day by intravenous infusion for 10 days total and then subjects will be monitored for up to 5 years to assess efficacy and safety endpoints. Subjects who do not respond to initial cycle or relapse may receive a second cycle of drug after the 3 month time point.

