8.2 Secondary Endpoints

8.2.1 Transfusion-Independence for red blood cells and/or platelets

8.2.2 Overall survival. In comparing the probabilities of survival between responders and non-responders, the baseline time is set to be 3 months after first dose alemtuzumab at which response is determined for the primary endpoint.

8.2.3 Life Threatening Toxicity. Subjects who do not complete the treatment course because of toxicity or voluntary withdrawal will be included in analyses.

8.2.4 Relapse-free survival is defined as the time elapsed between time of documented response to Campath and evidence for relapse. Relapse is defined as a fall in peripheral blood counts to 50% the values obtained during the response period.

8.2.5 Molecular Response to Campath is defined as disappearance of the clonal population of T-LGL

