8.4 Statistical Methods

The planned analyses will include descriptive statistics on the proportions of responses (i.e. % subjects with partial or complete response) and the time to response. The response probabilities will be estimated using the sample proportions and their inferences including confidence intervals and hypotheses testing will be evaluated using Binomial distributions.

The time to responses and the relapse-free survival will be analyzed using appropriate tools in survival analysis, such as cumulative incidence estimate and Cox regression type analysis for covariates, which takes into consideration both death without the event of interest as a complete risk and random censoring due to loss of follow-up. The Kaplan-Meier estimates and Cox regression will be used to evaluate the treatment effects on the overall survival. Graphical tools will be used to display the appropriate estimates (i.e. estimated proportions, the cumulative incidence curves, Kaplan-Meier curves) and their corresponding 95% confidence intervals.

Methods based on multiple regression, analysis of variance, and logistic regression will also be employed if deemed appropriate.

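### Relapse-free survival has no rule for a new T-LGL drug started before counts halve, and is overstated when that drug is started because the response is waning

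*Combined protocol and SAP*

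**What the plan says.** Section 8.2.4 gives the endpoint: "Relapse-free survival is defined as the time elapsed between time of documented response to Campath and evidence for relapse". It then gives the only event: "Relapse is defined as a fall in peripheral blood counts to 50% the values obtained during the response period". Starting another drug is not mentioned there.

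Section 8.4 proposes cumulative incidence and Cox-type methods for this endpoint, using an analysis that "takes into consideration both death without the event of interest as a complete risk and random censoring due to loss of follow-up". No other competing event and no other kind of censoring is named.

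Section 8.6 lists, among the grounds for removal by the principal investigator, "Initiation of additional immunosuppressive therapy (except steroids or CsA"). Subjects who are removed "will be asked to continue to have labs monitored through the 6 month off drug time point", for safety purposes. Section 3 plans much longer follow-up: "subjects will be monitored for up to 5 years to assess efficacy and safety endpoints".

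The two exempt drug classes are described as active in this disease. On cyclosporine, Section 2.2 reports that "we treated 25 T-LGL patients with oral cyclosporine and response was observed in about half of the patients". Section 2.4 includes corticosteroids among the agents that produce responses.

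**The concern.** Relapse is read from counts alone, so the endpoint cannot separate a response that still rests on alemtuzumab from one held up by a later drug. Nor does the plan say what happens to a responder who leaves because of a later drug. If the drug was started because the response was failing, that subject has a higher risk of relapse than those still followed, and censoring is then informative.

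Section 2.4 justifies the trial partly by the hope of longer remission and fewer relapses than with existing agents. Relapse-free survival is the endpoint that speaks to that hope. With about 20 responders expected (39 × 0.50 = 19.5, from Section 8.3), the handling of a few subjects moves the curve.

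**Working it through.** **The plan's own figures.** The documents state no figure for relapse-free survival. The only design calculation, in Section 8.3, is for 3-month response. It reproduces (6/19 then 16/39: exact alpha 0.0455, power 0.8036) but does not bear on this point.

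**Step 1: can treatment plausibly come before a recorded relapse?** Inputs are the entry thresholds (Section 4.1.3), the partial-response rules (Section 8.1) and the 50% rule (Section 8.2.4). Relapse level = 0.5 × response value.

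| Line | Entry threshold | Example response | Relapse level |
|---|---|---|---|
| Hemoglobin | < 9 g/dL with symptoms | 8 to 10 g/dL | 5 g/dL |
| Neutrophils | < 500/µL | 250 to 600/µL | 300/µL |
| Platelets | < 20,000/µL | 9,000 to 22,000/µL | 11,000/µL |

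The relapse level falls below the entry threshold whenever the response value is under 18 g/dL (2 × 9), 1,000/µL (2 × 500) or 40,000/µL (2 × 20,000) respectively. For neutrophils and platelets, a partial response requires at least doubling, so the relapse level is not below the subject's own baseline. For hemoglobin it can be, as in the example (5 against 8). A subject can thus meet an entry criterion again and still count as relapse-free. After 6 months the scheduled blood counts are annual (Section 6.5), so a drug can also start between them.

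**Step 2: what happens next under the text?**
- Steroids or cyclosporine: exempt under Section 8.6, so the subject stays on study. Section 8.1 excludes growth factor and transfusion support from a response but does not mention these drugs. If they hold the counts up, no relapse is recorded. If they hold them for a time, relapse is recorded late.
- Another immunosuppressant: the subject may be removed. Labs are requested to 6 months off drug. If response is documented at the 3-month assessment, that covers roughly the first 3 months of relapse-free time, against follow-up of up to 5 years. No censoring rule for removal is written, and "random censoring due to loss of follow-up" is the only kind named.

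**Step 3: direction and illustrative size.** Let S be true freedom from loss of response at some horizon, and f the share of losses that first appear as a new drug. Both are assumptions. Times are exponential and deaths are ignored.

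- Censored at drug start: apparent value = S^(1−f).
- Kept on study as relapse-free: apparent value = 1 − (1−f)(1−S).

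| S = 50% | Censored | Kept relapse-free |
|---|---|---|
| f = 10% | 0.5^0.9 = 53.6% | 1 − 0.9 × 0.5 = 55.0% |
| f = 20% | 0.5^0.8 = 57.4% | 1 − 0.8 × 0.5 = 60.0% |
| f = 30% | 0.5^0.7 = 61.6% | 1 − 0.7 × 0.5 = 65.0% |

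A simulation of 400,000 exponential times for the censored case gave 53.6%, 57.5% and 61.6%. At f = 25%, other values of S give the same direction: S = 70% becomes 76.5% or 77.5%, and S = 30% becomes 40.5% or 47.5%.

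**Step 4: when is there no such bias?** If the drug is started independently of relapse risk, censoring does no harm. The simulated estimate was 49.8% against a true 50%.

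**The case against.** Much of the opposing case stands, and it limits the point.

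- A reader might infer that the plan treats every exit as random censoring. It does not say so. Section 8.6 lists loss to follow-up and new immunosuppression as separate items, and Section 8.4 offers its methods as examples. Censoring is inferred because no other handling is named.
- A reader might infer that counts stop at removal. Section 8.6 asks for labs to 6 months off drug, and Section 9.3 brings in home-physician results, so some relapses could still be seen, though on the new drug.
- A reader might infer that steroids or cyclosporine hide every relapse. Section 2.2 puts the cyclosporine response at about half. If the drug holds counts in only half of such subjects, the kept-relapse-free value at S = 50%, f = 25% drops from 62.5% to 1 − 0.875 × 0.5 = 56.25%, ignoring delay.
- A reader might infer that the error always favours alemtuzumab. Section 2.1 notes an association with rheumatoid arthritis, so a drug may be started for another reason, and Step 4 shows no censoring bias in that case.
- Section 5.2 allows a second alemtuzumab cycle on relapse, which may reduce the share who turn first to another drug. That share is unknown.
- Censoring exactly at the moment of failure is the extreme case. With 20 responders, a 50% estimate has a 95% half-width of about 22 points (1.96 × √(0.25/20)), wider than the illustrated shifts of 4 to 12 points.

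The last point does not remove the concern: the interval reflects chance, whereas this shift is systematic and would remain with more subjects.

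**Conclusion.** The concern holds in a limited form. The count-only definition, with a threshold that can lie below entry severity, leaves room for a waning responder to start another T-LGL drug before relapse is recorded. On steroids or cyclosporine that subject may be credited as relapse-free, or relapse late. On another agent the subject may leave, and outcome-dependent censoring is the likely, though unwritten, handling. Relapse-free survival is overstated when the drug is started because the response is waning; a drug started for an unrelated reason need not cause this bias.

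The size cannot be found from the documents. The illustration of about 54–62% for a true 50% rests on assumed values: 10–30% of failures appearing first as new treatment, all censored at that moment, and no deaths. A reader might also infer that the trial's main conclusion is at risk. It is not: this is a secondary endpoint with no hypothesis or threshold attached, and the two-stage decision on 3-month response is unaffected. The change is worth making but is not a condition for the primary analysis.

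**What to change.** - **Section 8.2.4:** count the start of any new systemic treatment given for T-LGL after a response, including steroids or cyclosporine given for T-LGL, as an event at its start date. Record the reason for treatment.
- **Section 8.4:** limit non-informative censoring to end of follow-up and losses unrelated to disease. Report the count-only definition as a sensitivity analysis.

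This concerns only how the endpoint is scored and does not alter treatment or the grounds for removal.

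**Cost.** It needs wording in two sections and a field for the reason for treatment. Progress notes, including those from home physicians, are already abstracted under Section 9.3 and should supply the start dates. Relapse-free survival will look somewhat shorter. Whether a drug was given for T-LGL is an open-label judgement, so the sensitivity analysis should be reported beside the main result.

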5.3 Pre-medications and management of infusion reactions

Subjects will receive pre-medication with oral diphenhydramine 50 mg and acetaminophen 650 mg 30 minutes prior to infusion.

Infusions reactions will be treated symptomatically (e.g., anti-emetics, IV fluid hydration, acetaminophen, antihistamines, inhaled bronchodilators).

In case of moderate or severe reactions hydrocortisone will be given and the infusion will be discontinued and restarted at a slower rate once the symptoms have subsided.

If a subject has a persistent severe infusion reaction to alemtuzumab (Campath®) that does not respond to measures to ameliorate the signs/symptoms associated to the infusion, the infusion will be discontinued and the subject will be followed for 6 months then taken off study (see section 9.6).

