9.2.2 Adverse Events Management

. The AEs will be attributed (unrelated, unlikely, possibly, probably or definitely) to study medication and/or disease. AEs will be graded by severity utilizing CTC version 2.0. A copy of the criteria can be down-loaded from the CTEP home page at <http://ctep.cancer.gov/reporting/ctc.html>.

Abnormal laboratory findings used to evaluate the safety of this protocol regimen will be collected to include any change from laboratory assessments done prior to first dose of study medication that result in a progression to a grade 3 or 4 laboratory toxicity. The laboratory toxicities will be attributed (unrelated, unlikely, possibly, probably or definitely) to study medication and/or disease. They will be graded by severity utilizing CTC version 2.0.

Length of Adverse Event reporting: Adverse event collection will continue for 6 months after the last dose of Campath after which the events will be recorded in the medical record but not abstracted to toxicity tables. Serious adverse event reporting will continue as long as the subject remains on study.

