9.2.4.1 Reporting Timeframes to IRB Chair, Clinical Director, and/or NHLBI IRB

Serious Events

Reports to the IRB and CD: The PI must report Serious UPs, and Serious PDs to the IRB and CD as soon as possible but not more than 7 days after the PI first learns of the event using the NIH Problem Report Form.

Reports to the IRB Chair and CD: The PI must report all SAEs that do not meet the definition of UP to the IRB chair and CD not more than 14 days after the PI first learns of the event, using the NIH Problem Form.

Non-serious Events

Reports to the IRB and CD: The PI must report all UPs that are not Serious to the IRB and CD, and PDs that are not Serious to the IRB, not more than 14 days after the PI first learns of the event using the NIH Problem Form.

Deaths

The PI must report all deaths (that are not UPs) to the CD as soon as possible, but not more than 7 days after the PI first learns of the event

9.2.4.2 At continuing review, the PI will provide to the IRB a summary of:

- All UPs
- All PDs
- All AEs (except for those granted a waiver of reporting)
- If, while preparing the continuing review, the PI identifies a greater frequency or level of severity of expected adverse events than was previously identified in the protocol or investigational brochure (IB), these should be reported separately as a UP. If such an observation occurs before the time of continuing IRB review, it should be reported to the IRB and CD as a UP in the time frames noted above, and summarized at the time of continuing review.

Exclusions to data reporting:

The following Adverse Events will be captured only in the source documents and will not be reported to the IRB at the time of continuing review.

- Laboratory values that do not meet the definition of AE
- All grade 1 events listed as expected in the investigator's brochure, package insert or the protocol.

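### Section 8.6 can take non-responders off study with no visible plan to learn whether they later die, although survival is compared by response (minor)

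*Combined protocol and SAP*

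**What the plan says.** Section 8.6 is headed as off-study criteria. Under investigator decision, however, its lead-in is a drug-stop rule: alemtuzumab is discontinued and "the subject will be followed until the event has resolved". The list below it mixes drug-stop reasons (infusion intolerance, hypersensitivity) with study-exit reasons (loss to follow-up, study completion). It also includes "Failure to respond to Campath therapy", which has no point of resolution. The closing paragraph treats the list as removal from the study. Subjects who withdraw or are removed "will be asked to continue to have labs monitored through the 6 month off drug time point", for safety purposes, and once off study are referred back or offered another branch protocol.

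Related passages:

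- 5.3, on persistent severe infusion reactions: "the infusion will be discontinued and the subject will be followed for 6 months then taken off study (see section 9.6". There is no section 9.6; the off-study criteria are in 8.6.
- 5.2 lets non-responders have a second cycle at the investigator's discretion any time after month 3, and 8.2.7 makes response to it a secondary endpoint.
- 9.2.2: "Serious adverse event reporting will continue as long as the subject remains on study".
- 9.2.4.1: "The PI must report all deaths (that are not UPs) to the CD as soon as possible", with the clock starting when the investigator learns of the death.
- Section 3: "subjects will be monitored for up to 5 years to assess efficacy and safety endpoints". Section 6.5 sets yearly Clinical Center visits for 5 years.
- 8.2.2: "In comparing the probabilities of survival between responders and non-responders, the baseline time is set to be 3 months after first dose alemtuzumab". Section 8.4 analyses overall survival by Kaplan-Meier and Cox regression.

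**The concern.** The variable that defines the two groups in the 8.2.2 survival comparison is also a listed ground for leaving the study. After removal, the available text offers only requested laboratory monitoring to 6 months off drug. Serious adverse event reporting ends with study participation. The death report depends on the investigator happening to hear of the death, and enrolment in another protocol is only a possibility. Section 8.4 mentions only random loss to follow-up, in its sentence on time to response and relapse-free survival, and has no provision for removal that depends on response.

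Two consequences follow if non-responders are removed.

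- The landmark comparison loses events in one group. This is mainly a loss of precision. It becomes bias only if, among non-responders, those removed differ in prognosis from those kept.
- Pooled Kaplan-Meier survival is overstated if non-responders die faster than responders, because the subjects still followed are then increasingly responders.

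Separately, 8.6 does not say whether failure to respond means after one cycle or after all cycles, so it does not fit cleanly with 5.2.

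**Working it through.** The plan gives no figure for this loss, so the size has to be illustrated.

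**Inputs from the protocol.** Four-year mortality m = 10% to 20% (section 2.1); landmark at month 3 (8.2.2); follow-up to month 60 (sections 3 and 6.5); n = 39, with response rates of 30% and 50% (8.3).

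**Assumptions not in the documents.** Constant hazards; non-responder to responder hazard ratio (HR) of 1, 2 or 3; share s of non-responders removed; last information at month L = 6. At 50% response, 39/2 = 19.5, taken as 20 per group.

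**Formulas.**

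- Responder monthly hazard h solves 0.5·exp(−48h) + 0.5·exp(−48·HR·h) = 1 − m. The non-responder hazard is k = HR·h.
- Expected non-responder deaths, months 3-60: 20·(1 − exp(−57k)). Responders: the same with h.
- Non-responder deaths seen: 20s·(1 − exp(−(L−3)k)) + 20(1−s)·(1 − exp(−57k)).
- SE of the log hazard ratio ≈ √(1/d_nonresp + 1/d_resp).
- Pooled Kaplan-Meier at month 60 = S(L) × survival from L to 60 among those still followed. Overstatement = that value minus S(60).

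**Worked case, m = 20%, HR = 3, s = 0.5.** h = 0.002393 and k = 0.007179.

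- Non-responder deaths expected: 20·(1 − 0.664) = 6.72. Seen: 10·0.0213 + 10·0.336 = 3.57, or 53%.
- SE: √(1/6.72 + 1/2.55) = 0.736 in full; √(1/3.57 + 1/2.55) = 0.820 with loss; ratio 1.11.
- S(6) = 0.4929 + 0.4789 = 0.9718. Survival from 6 to 60 among those followed: (0.4331 + 0.1625)/(0.4929 + 0.2395) = 0.8133. Kaplan-Meier: 0.9718 × 0.8133 = 0.790. True S(60): 0.758. Overstatement: 3.2 points.
- Binomial SE of S(60) at n = 39: √(0.758·0.242/39) = 0.069, so the bias is 0.47 SE.

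**All cases, 50% response, loss at month 6.**

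| m | HR | Non-resp. deaths | Resp. deaths | SE(log HR), full | Non-resp. deaths seen, s = 0.5 | Overstatement (points), s = 0.25 | s = 0.5 | s = 1 |
|---|---|---|---|---|---|---|---|---|
| 10% | 1 | 2.35 | 2.35 | 0.92 | 1.24 | 0 | 0 | 0 |
| 10% | 2 | 3.09 | 1.61 | 0.97 | 1.63 | 0.50 | 1.16 | 3.47 |
| 10% | 3 | 3.46 | 1.23 | 1.05 | 1.83 | 0.75 | 1.75 | 5.22 |
| 20% | 1 | 4.66 | 4.66 | 0.66 | 2.47 | 0 | 0 | 0 |
| 20% | 2 | 6.02 | 3.28 | 0.69 | 3.19 | 0.91 | 2.13 | 6.34 |
| 20% | 3 | 6.72 | 2.55 | 0.74 | 3.57 | 1.39 | 3.23 | 9.59 |

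Across these cases, about 76% of non-responder deaths are seen if a quarter are removed and 53% if half are. The SE of the log hazard ratio rises by 4%-7% or 11%-20%.

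**Other settings.** With L = 12, after a possible second cycle, the largest overstatements are 1.2, 2.9 and 8.4 points for s = 0.25, 0.5 and 1. At 30% response (39 × 0.7 ≈ 27 non-responders), weights 0.3 and 0.7 replace 0.5 and 0.5. For m = 20% and HR = 3, h = 0.00197, and removing all non-responders gives 0.9721·exp(−54h) = 0.874 against a true 0.757, about 11.6 points. Removing half gives about 2.7 points.

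No SE ratio is given for s = 1. Only 0.13-0.43 non-responder deaths would then be seen, and the large-sample formula fails below one event.

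**The case against.** The strongest reply is that the protocol as a whole keeps non-responders on study. The operative instruction in 8.6 stops the drug and continues follow-up. Sections 3 and 6.5 are not limited to responders. Section 5.2 re-treats non-responders, 8.2.7 evaluates that re-treatment, and 8.2.2 presupposes survival data on non-responders. The list's inclusion of loss to follow-up and study completion suggests loose template drafting. Much of this stands: removal is at the investigator's discretion, and a non-responder who is not removed stays on the yearly visits. It does not dispose of the closing paragraph of 8.6, which provides for subjects removed by investigator decision and ends their planned contact at 6 months off drug.

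A second reply is that the landmark comparison is weak anyway. This also stands. With complete follow-up the SE of the log hazard ratio is already 0.66-1.05, a 95% interval of about 3.6-fold to 7.8-fold either way (exp(1.96 × 0.655) and exp(1.96 × 1.05)). A rise of 11%-20% would change few conclusions.

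A third is that part of the text between 9.2.3 and 9.2.4.1, and the consent pages, are not available here and might contain a provision. The point is therefore limited to the available text.

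A reader might also infer that 8.6 orders every non-responder off study, or that the survival comparison is necessarily biased. The documents support neither. The first ignores the investigator's discretion and 5.2; the second needs removed non-responders to differ in prognosis from those kept.

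**Conclusion.** The point holds as a minor one. Section 8.6 does not separate stopping drug from leaving study, names non-response as a ground, and is not backed in the available text by any planned vital-status contact after removal. Survival data can therefore be lost because of response status.

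On the stated assumptions, with up to half of non-responders removed, the effect is a modest loss of precision in an already imprecise comparison and an overstatement of pooled 5-year survival of at most about half a standard error. The documents give neither the hazard ratio nor the share removed. The bias is zero at a hazard ratio of 1 or if nobody is removed. The 9.6-point and 11.6-point figures (50% and 30% response) need every non-responder to leave, an extreme case that fits poorly with 5.2. Nothing here touches the 3-month primary endpoint, the two-stage rule, n = 39 or the 8.5 stopping rule.

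**What to change.** In 8.6, list off study treatment and off study separately. State that stopping treatment, or removal by investigator decision (including for non-response), does not end survival follow-up. Collect vital status and date of death yearly to 5 years, by telephone or home-physician contact, for every treated subject unless consent is withdrawn.

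Reconcile 8.6 with 5.2 (which cycle's failure counts) and with 5.3, including its pointer to a section 9.6 that does not exist. Which treatment rule should hold is for the sponsor and investigator to settle, not this review.

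The cost is a short amendment, matching consent wording, and one brief contact a year for each subject who has left.
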